5.3.2. Continuous Endpoints

For non-PRO continuous endpoints measured longitudinally, missing values post-baseline will not be imputed explicitly. For such endpoints, assuming that the missing data mechanism is missing at random (MAR), the data will be analyzed based on a restricted maximum likelihood (REML) using a linear mixed-effect model with repeated measures for these continuous variables (see [Section 5.2.3](#)). This model will yield valid inferences in the presence of a missing data mechanism that is MAR.

For the continuous PRO variables such as pruritus NRS, DLQI, POEM, PSAAD, HADS, and EQ-5D-5L, rules suggested by the developers of these instruments will be followed in calculating the missing values. If these rules are not enough for imputing a value, then the missing values will be handled in the same way as non-PRO variables.

5.3.3. Time to Event Endpoints

For time-to-event endpoints, subjects who complete the study without the event of interest or those who withdraw before experiencing the event of interest will have their event times right censored at the last available measurement time (or visit) used to define whether the subject experienced the associated event (ie, the event of interest is presumed to have occurred beyond this time point).

6. ANALYSES AND SUMMARIES

Unless specifically noted otherwise, the analyses specified in [Section 6](#) will be included in the Week 16 Analysis. The Week 16 Analysis contains data up to and including Week 16 Visit Date. The definition of data cut for the analysis is detailed in [Appendix 2](#). For all endpoints, comparisons will be done pairwise between each active treatment group (PF-04965842 200 mg QD, PF-04965842 100 mg QD and dupilumab) and placebo (three separate tests of hypotheses). For the Week 16 Analysis, the two placebo sequences will be combined into one group. Pairwise analyses with point estimates of the difference and the associated 95% confidence intervals will also be done among the active treatment groups

PF-04965842 200 mg QD, PF-04965842 100 mg QD and dupilumab. P-value will only be presented for the PF-04965842 doses vs. placebo (except for NRS4 at Week 2 and Days 2-15 where p-value for PF-04965842 doses vs. dupilumab will also be presented, see [Section 5.1](#)).

For the End of Study Analysis which contains additional data after the final database release, the two placebo sequences will not be combined.

A summary of analyses for clinical efficacy endpoints is provided in [Appendix 1](#). Visit windows to be used for all efficacy analyses and some relevant safety analyses are detailed in [Appendix 2](#).

6.1. Co-primary Endpoint - Week 12 IGA Response

6.1.1. Primary Analysis

- Summary: Proportion of subjects achieving IGA response at Week 12;
- Population: FAS;
- Statistical Method: CMH and normal approximation in [Section 5.2.1](#);
- Missing Data: Missing data arising due to subject dropout are considered “non-response” (see [Section 5.3.1](#)).

6.1.2. Additional/Supportive Analysis

Additional analyses of the Week 12 IGA response are:

- The proportion of subjects achieving IGA response at Week 12 will be analyzed using the CMH and normal approximation method in [Section 5.2.1](#) for the PPAS population.
- Results of proportion of subjects achieving the IGA response at Week 12 will be obtained from the FAS population using a tipping point analysis where all missing responses will be multiply imputed (which will consider analyses under MAR as well as MNAR as described in [Section 5.3.1](#) and [Appendix 3](#)).

6.2. Co-primary Endpoint - Week 12 EASI-75 Response

6.2.1. Primary Analysis

- Summary: Proportion of subjects achieving EASI-75 response at Week 12;
- Population: FAS;
- Statistical Method: CMH in [Section 5.2.1](#);
- Missing Data: Missing data arising due to subject dropout are considered “non-response” (see [Section 5.3.1](#)).

6.2.2. Additional/Supportive Analyses

Additional analyses of the Week 12 EASI-75 response are:

- The proportion of subjects achieving EASI-75 response at Week 12 will be analyzed using the CMH and normal approximation method in [Section 5.2.1](#) for the PPAS population.
- Results of proportion of subjects achieving the EASI-75 response at Week 12 will be obtained from the FAS population using a tipping point analysis where all missing responses will be multiply imputed (which will consider analyses under MAR as well as MNAR as described in [Section 5.3.1](#) and [Appendix 3](#)).

6.3. Key Secondary Efficacy Endpoints

6.3.1. Week 2 NRS4 for severity Response

- Summary: Proportion of subjects with NRS4 for severity response at Week 2; Week 2 NRS value is based on visit window ([Appendix 2](#));
- Population: Subjects from the FAS with a baseline NRS score for severity ≥ 4 ;
- Statistical Method: CMH and normal approximation in [Section 5.2.1](#). In addition to comparisons versus placebo, tests of hypotheses will also be performed (with p-values reported) for comparing this endpoint between PF-04965842 200 mg QD and dupilumab as well as between PF-04965842 100 mg QD and dupilumab;
- Missing Data: Missing data arising due to subject dropout are considered “non-response” (see [Section 5.3.1](#)).

6.3.2. Week 16 IGA Response

- Summary: Proportion of subjects achieving IGA response at Week 16;
- Population: FAS;
- Statistical Method: CMH and normal approximation in [Section 5.2.1](#);
- Missing Data: Missing data arising due to subject dropout are considered “non-response” (see [Section 5.3.1](#)).

6.3.3. Week 16 EASI-75 Response

- Summary: Proportion of subjects achieving EASI-75 response at Week 16;
- Population: FAS;
- Statistical Method: CMH in [Section 5.2.1](#);

- Missing Data: Missing data arising due to subject dropout are considered “non-response” (see [Section 5.3.1](#)).

6.4. Secondary Efficacy Endpoints

6.4.1. Binary Endpoints

- Endpoints:
 - Weeks 2, 4 and 8 IGA, EASI-75 Response;
 - NRS4 for Severity Response each day from Days 2-15, Weeks 4, 8, 12 and 16;
 - Weeks 2, 4, 8, 12 and 16 EASI-50, EASI-90, EASI-100, SCORAD50, SCORAD75.
- Summary: Proportion of subjects with response at each specified time points;
- Population: FAS; Subjects from the FAS with a baseline NRS score for severity ≥ 4 will be used for NRS4 analysis;
- Statistical Method: CMH and normal approximation in [Section 5.2.1](#). P-value for PF-04965842 doses vs. dupilumab will also be presented for Days 2-15 NRS4;
- Missing Data: Missing data arising due to subject dropout are considered “non-response” (see [Section 5.3.1](#)).

6.4.2. Time to Achieve NRS4 for severity

- Summary: Time to achieve NRS4 for severity from baseline;
- Population: Subjects from the FAS with a baseline NRS score for severity ≥ 4 ;
- Statistical Method: Analyses for Time to Event Data in [Section 5.2.5](#);
- Missing Data: See [Section 5.3.3](#).

6.4.3. Continuous Endpoints

- Endpoints:
 - Weeks 2, 4, 8, 12 and 16 Change from Baseline and Percent Change from Baseline in % BSA, Total SCORAD score, SCORAD subjective assessments of sleep loss (VAS);
 - Weeks 2, 4, 8, 12 and 16 Percent Change from Baseline in Total EASI Score;
 - Percent Change from Baseline in Severity of Pruritus NRS each day from Days 2-15, Weeks 4, 8, 12 and 16;

- Summary: Change from baseline and/or percent change from baseline at each specified time points;
- Population: FAS;
- Statistical Method: MMRM in [Section 5.2.3](#);
- Missing Data: Observed Data.

6.4.4. Week 16 Corticosteroid-free days

- Summary: Number of days when neither topical or systemic corticosteroids¹ was taken (from Day 1 up to Week 16/Day 116 during the study treatment exposure period);
- Population: FAS;
- Statistical Method: ANCOVA in [Section 5.2.2](#);
- Missing Data: Observed Data.

6.5. PRO Endpoints

6.5.1. Continuous Endpoints

- Endpoints:
 - Weekly Change from Baseline (up to Week 16) in Total PSAAD Score;
 - Weeks 2, 4, 8, 12, and 16 Change from Baseline in PtGA;
 - Weeks 2, 12 and 16 Change from Baseline in DLQI;
 - Weeks 12 and 16 Change from Baseline in HADS (separate for anxiety and depression), POEM, EQ-5D-5L;
- Summary: Change from Baseline for each specified time points;
- Population: FAS;
- Statistical Method: MMRM in [Section 5.2.3](#). As PSAAD is collected daily, data will be summarized weekly using a simple average of the values recorded within a week;
- Missing Data: Observed Data.

090177e1937d0b4e\Approved\Approved On: 18-May-2020 15:17 (GMT)

CCI

6.7. Subset Analyses

Summary statistics for co-primary endpoints will be presented by subgroups below.

- Age (years) group (<40, ≥40; <65, ≥65);
- Sex (Male, Female);
- Race (White, Black or African-American, Asian, Other²);
- Region of enrollment (US/Canada/Australia, Europe, Asia, Latin America);
- Weight (kg) (less than or equal to the median value in FAS, above the median value);
- AD Duration (years) group (<26, ≥26);
- Baseline disease severity (moderate, severe);
- Baseline EASI group (16-25, >25);
- Baseline % BSA group (10-30, >30-50, >50);
- Previous use of systemic immunosuppressant for AD (Yes, No).

Estimates of the response of and all pairwise difference between the PF-04965842 200 mg QD, PF-04965842 100 mg QD and placebo, along with the 95% confidence interval (no p-value), will be presented for each defined category of each subgroup. For the binary endpoints, analyses will be performed using normal approximation without any adjustments for baseline disease severity.

The primary purpose of the subgroup analyses is to check for consistency of results across subgroups, to make sure overall results are not being driven by some subset of subjects.

Graphical display (eg, forest plots) of the differences between treatment groups will be presented. There is no intention to have any specific inference within subgroups.

6.8. Baseline and Other Summaries and Analyses

6.8.1. Baseline Summaries

Demographics, medical history, primary diagnosis, history of prior AD treatments and disease characteristics including variables defined in [Section 3.4](#) will be summarized by treatment group according to CaPS. Baseline disease severity based on IGA and baseline EASI score will also be summarized by gender.

6.8.2. Study Conduct and Subject Disposition

Subjects evaluation, disposition, discontinuation will be summarized according to CaPS.

² For purposes of analysis, Other will comprise the categories of American Indian or Alaska Native, Native Hawaiian or Other Pacific Islander, Multi-Racial and any other category reported on the CRF.

6.8.3. Study Treatment Exposure

6.8.3.1. Oral Dosing

- Duration of Treatment is defined as the total number of dosing days on which study drug was actually administered; if N doses missed on unknown dates, it reduces the Duration of Treatment by N/2 (when N is an even number) or (N-1)/2 (when N is an odd number);
- Exposure Time is defined as the total number of days from first to and including last day of study oral dosing (Last Oral Dosing Date - First Oral Dosing Date + 1);
- Dose Compliance is defined as the number of doses of study drug the subject took out of the expected total number of doses of study drug.
 - Expected Number of Doses = 2*(Exposure Time);
 - Dose Compliance = (Total Actual Oral Pills/ Expected Number of Doses) * 100%.

Investigational product may be temporarily withheld for a maximum of 14 days at investigator's discretion due to abnormal laboratory tests or adverse event (Protocol Section 5.3). The Dose Compliance does not consider whether missed doses were due to protocol-allowed temporary withholding.

Number, mean, standard deviation, median, minimum and maximum will be presented for those variables: Duration of Treatment, Exposure Time and Dose Compliance. Number and percent will be reported for subjects in Duration of Treatment categories, and Dose Compliance <80% and Dose Compliance >120%.

6.8.3.2. Injection Dosing

Dupilumab or its matching placebo is administered every other week from Day 1 to Week 14, with two loading doses at baseline and then one dose each time.

- Exposure Time of Injection = (Last Injection Date - First Injection Date + 14); Eg, for subject receiving only the loading doses at baseline, the Exposure Time of Injection should be 14 days;

090177e1937d0b4e\Approved\Approved On: 18-May-2020 15:17 (GMT)

- Expected Number of Injections (Cumulative) will be based on Last Injection Date relative to Day 1/Baseline, using the following table:

Injection Schedule	Target Day	Window	Expected Number of Injections (Cumulative)
Baseline	Day 1	Days 1 to 7	2
Week 2	Day 15	Days 8 to 21	3
Week 4	Day 29	Days 22 to 35	4
Week 6	Day 43	Days 36 to 49	5
Week 8	Day 57	Days 50 to 63	6
Week 10	Day 71	Days 64 to 77	7
Week 12	Day 85	Days 78 to 91	8
Week 14	Day 99	Days 92 to -	9

- Eg, if a subject receives his/her last injection on Day 76, the Expected Number of Injections (Cumulative) should be 7.
- Injection Dose Compliance = (Number of Injections Received / Expected Number of Injections) * 100%.

Number, mean, standard deviation, median, minimum and maximum will be presented for those variables: Exposure Time of Injection, Number of Injections Received, Injection Dose Compliance. Number and percent will be reported for with Injection Dose Compliance <80% and Injection Dose Compliance >120%.

6.8.4. Concomitant/Background Medications and Non-Drug Treatments

Prior drug and non-drug treatment, concomitant drug and non-drug treatment will be summarized according to CaPS.

6.8.4.1. Background Topical Therapy (Medicated and Non-Medicated)

Number and percent of subjects used non-medicated emollient, medicated topical therapy, topical corticosteroids (TCS), topical calcineurin inhibitors (TCI), topical PDE4 inhibitors will be reported during the study treatment exposure period.

Subjects must comply with standardized background topical therapy guidance throughout the study (Protocol Section 5.9.1). “Did the subject conform to background therapy per protocol” is ‘No’ when medication should have been used per protocol and was not used OR if medication was used but did not meet protocol requirements.

- Exposure Time (of study treatment) is defined as the total number of days from first to and including last day of study dosing (Last Dosing Date - First Dosing Date + 1);

090177e1937d0b4eApproved\Approved On: 18-May-2020 15:17 (GMT)

- During the period of first dosing date to last dosing date, if any use of TCS, TCI or PDE4 inhibitor is non-compliance with protocol (ie, “No” is entered for “Did the subject conform to background therapy per protocol”), the compliance for that day is “No”;
- Medicated Topical Therapy Compliance = $1 - (\text{Days non-compliant with background topical} / \text{Exposure Time}) * 100\%$.

Number, mean, standard deviation, median, minimum and maximum will be presented for Medicated Topical Therapy Compliance. Number and percent will be reported for subjects with compliance of medicated topical therapy < 80%.

6.8.4.2. Protocol Prohibited Therapy for Primary Diagnosis

Number and percent will be reported for subjects used protocol prohibited therapy for AD: high potency TCS, systemic medication for AD, phototherapy during the period of first dosing date to last dosing date.

6.9. Safety Summaries and Analyses

Safety analysis will be based on the SAF analysis set.

All clinical AEs, SAEs, treatment-emergent signs and symptoms (TEAEs), withdrawal due to AEs, ECGs, vital signs and safety laboratory data will be reviewed and summarized on an ongoing basis during the study to evaluate the safety of subjects.

Safety data will be presented in tabular and/or graphical format and summarized descriptively, where appropriate. All safety endpoints will be listed and summarized in accordance with CaPS. Categorical outcomes (eg, AEs) will be summarized by subject counts and percentage. Continuous outcome (eg, blood pressure, pulse rate, etc.) will be summarized using N, mean, median, standard deviation, etc. Change from baseline in laboratory data, ECGs, physical exams and vital signs will also be summarized. Subject listings will be produced for these safety endpoints accordingly.

6.9.1. Adverse Events

The safety data will be summarized in accordance with CaPS. All safety data will be summarized descriptively through appropriate data tabulations, descriptive statistics, categorical summaries, and graphical presentations. Safety endpoints for the study include:

- Treatment-emergent AEs and SAEs;
- Withdrawals from active treatment due to AEs;
- Serious infections, defined as any infection (viral, bacterial, and fungal) requiring hospitalization or parenteral antimicrobials;

Treatment-emergent AEs will also be analyzed using a 3-tier approach. Risk differences between the active treatments and placebo will be used to summarize the results.

For Tier-1 events, point estimates, 95% confidence intervals and p-values will be presented graphically comparing each active dose group with placebo. No multiplicity adjustments will be made. For Tier-2 events, only point estimates and 95% confidence intervals will be presented graphically (see [Section 5.2.6](#)). Tier-3 events will be summarized as part of the overall AE summaries, AEs will be displayed by MedDRA system organ class (SOC).

It should be recognized that most studies are not designed to reliably demonstrate a causal relationship between the use of a pharmaceutical product and an adverse event or a group of adverse events. Except for selected events in unique situations, studies do not employ formal adjudication procedures for event classification. CCI

[REDACTED]

6.9.2. Laboratory Data

Laboratory data will be listed and summarized in accordance with the CaPS reporting standards. Summaries of subjects meeting pre-specified monitoring and discontinuation criteria will be created using methods for categorical data (see [Section 5.2.4](#)).

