- Any bleeding event thought to be associated with a platelet count reduction per the judgement of the investigator (or, if necessary/desired, following discussion with sponsor).
- Adverse event, per judgment of the investigator, requiring discontinuation from treatment (or, if necessary/desired, following discussion with sponsor).
- Any adverse event or laboratory abnormality, that per the investigator's judgement requires withholding of investigational product for >14 days.

NOTE: any initial lab value below must be retested within 48 hours.

- Two sequential platelet counts <50,000/mm³. If the subject has a platelet count <25,000/mm³, investigational product should be temporarily withheld pending the confirmatory retest.
- Two sequential neutrophil counts <500/mm³.
- Two sequential lymphocyte counts <500/mm³.
- Two sequential hemoglobin assessments <8.0 g/dL or <30% from baseline value.
- Any of the following:
 - Two sequential AST or ALT elevations >3 times the upper limit of normal with at least one Total Bilirubin value >2 times the upper limit of normal.
 - Two sequential AST or ALT elevations >3 times the upper limit of normal with an abnormal INR.
 - Two sequential AST or ALT elevations >3 times the upper limit of normal accompanied by symptoms consistent with hepatic injury.
 - Two sequential AST or ALT elevations >5 times the upper limit of normal, regardless of Total Bilirubin or accompanying symptoms.

NOTE:

 Any of the above findings should prompt review of "The Potential Cases of Drug-Induced Liver Injury," Section 8.4.2 for which additional investigations must be conducted. • Two sequential increases in serum creatinine that are >50% over the average of screening and baseline values AND an absolute increase in serum creatinine ≥0.5 mg/dL. At the time of study completion or discontinuation, if a subject should exhibit elevations in serum creatinine ≥33% above the average of screening and baseline values, they will be re-tested every 1 to 2 weeks until the serum creatinine elevation is fully reversed to within 10% of the average of screening and baseline values or has stabilized.

Having met Discontinuation Criteria, the subject must be permanently withdrawn from treatment, have their end of treatment visit, and will then enter the 4-week follow-up period.

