Appendix 2. Definition and Use of Data Cut and Visit Windows in Reporting

For both the Week 16 Analysis and End of Study Analysis, a data cut at Week 16 drug dispensing visit will apply to each subject before the windowing. Only data from up to and including the Data Cut will be used for the Week 16 Analysis. Only data from after the Data Cut will be used for the End of Study Analysis. If a subject withdrew from the study and no drug was dispensed at Week 16, all available data for that subject will be included in the Week 16 Analysis.

Week 16 Analysis:

Visit Label	Target Day	Definition [Day window]
Screening		Days -28 to Day -1
Baseline	Day 1, Baseline	Day 1
Week 2	15	Days 2 to 22
Week 4	29	Days 23 to 43
Week 8	57	Days 44 to 71
Week 12	85	Days 72 to 99
Week 16	113	Days 100 to 120

End of Study Analysis:

Visit Label	Target Day	Definition [Day window]
Week 18	127	Days 121 to 134
Week 20	141	Days 135 to 155
Follow Up/End of Study		
Week 24	-	Days 156 to -

Visit windows will be used for efficacy variables, and for any safety data that display or summarize by study visit. For other endpoints (eg, ECG, vital signs), visit windows will be applied for summary statistics by study visits if required.

For the lab values, if the calculated study day for the labelled baseline visit is not study Day 1 but falls within 28 days before the start of the study dosing, then that data should be used for the baseline instead of leaving baseline missing.

For the other values, if the calculated study day for the labelled baseline visit is not study Day 1, but falls before the start of the study dosing, then that data should be used for the baseline instead of leaving baseline missing.

Observations on the actual day will be used to analyze Days 2-15 Pruritus NRS. Weeks 2, 4, 8, 16 Pruritus NRS will be based on the windowing method.

If two or more visits fall into the same window, keep the one closest to the Target Day. If two visits are equaled distant from the Target Day in absolute value, the later visit should be used.

Safety analysis may follow CaPS.

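### The Week 16 data cut separates a Week 16 abnormal laboratory value from its retest, so a two-value discontinuation case first abnormal at Week 16 is missing from the Week 16 table

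*SAP*

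**What the plan says.** SAP 6.9.2 (Laboratory Data): "Summaries of subjects meeting pre-specified monitoring and discontinuation criteria will be created using methods for categorical data". The criteria themselves are in protocol Appendix 4. A typical threshold-based laboratory discontinuation criterion there reads "Two sequential neutrophil counts <500/mm³". Platelets, lymphocytes, hemoglobin, AST/ALT (four variants) and serum creatinine also need two sequential values. A note above the list says that "any initial lab value below must be retested within 48 hours".

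SAP Appendix 2 says that, for both planned analyses, "a data cut at Week 16 drug dispensing visit will apply to each subject before the windowing". It then allocates the data: "Only data from up to and including the Data Cut will be used for the Week 16 Analysis", and "Only data from after the Data Cut will be used for the End of Study Analysis". It makes one exception. "If a subject withdrew from the study and no drug was dispensed at Week 16, all available data" go to the Week 16 Analysis.

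Protocol 9.6 and SAP section 5 rest the final clinical study report (CSR) on the Week 16 Analysis and put the End of Study results in a supplemental report. SAP 6.10.2 promises only some of the safety summaries at End of Study and does not name them.

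**The concern.** The table is meant to show, by treatment group, how many subjects met rules that require permanent discontinuation. To count a subject under a two-value rule, the program must find both values in the data it is allowed to read. At Week 16 the blood sample and the drug dispensing that defines the cut happen at the same visit (protocol 6.2.7). The sample is therefore the last laboratory record before the cut, and its retest is the first one after it. Nothing in the SAP rejoins the two.

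Two things are at stake. The discontinuation-criteria table in the main report is too low by every case first abnormal at Week 16. And placebo subjects start PF-04965842 at that visit (protocol 5.5), so the first value is a placebo value while the retest follows active dosing. The SAP does not say which treatment such a case belongs to.

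**Working it through.** The plan gives no figure on this point, so there is none to reproduce. The check is day arithmetic, a list of possible timelines, and a bound on the share affected.

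**1. Does the retest always fall after the cut?** The Week 16 visit is Day 113 ± 3, so Days 110 to 116 (protocol 6.2.7). A retest 1 to 2 days later falls between Day 110 + 1 = 111 and Day 116 + 2 = 118. For any given subject it is later than the visit, hence after the cut. This assumes that the retest is drawn on a later calendar day. A same-day repeat would be inside the cut.

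Days 111 to 118 also lie within the Week 16 window (Days 100 to 120) and before the first End of Study window (Day 121). The retest therefore has no End of Study visit label, but that affects only by-visit displays.

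**2. Does the exception rescue the case?** It needs both withdrawal from the study and no dispensing at Week 16. In the situation here the drug has been dispensed, and subjects who stop treatment stay in the study (protocol 6.4). It does not apply.

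**3. Which analysis sees a pair?** Take a Week 16 value and a retest that are both abnormal. Vary the Week 12 value and the end-of-treatment (EOT) value. The EOT visit is due within 1 week of the last dose and includes chemistry and hematology (protocol 6.4 and 6.2.9).

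| Week 12 | EOT | Uncut series | Week 16 data | End of Study data |
|---|---|---|---|---|
| normal | normal | pair | no pair | no pair |
| normal | abnormal | pair | no pair | pair (retest + EOT) |
| abnormal | normal | pair | pair (Week 12 + Week 16) | no pair |
| abnormal | abnormal | pair | pair | pair |

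The first two rows are the cases first abnormal at Week 16. Both are missing from the Week 16 table. The first is missing from the End of Study data as well. The second is counted there only if this table is among those produced.

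The last two rows should be rare. An abnormal Week 12 value needs its own retest within 48 hours. If that retest is abnormal, the criterion was already met before Week 16. If it is normal, it breaks the sequence. A Week 12 plus Week 16 pair therefore essentially requires a missed retest.

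**4. How large is the share?** The Schedule of Activities has post-baseline chemistry and hematology at Weeks 2, 4, 8, 12 and 16 up to the cut. If first abnormal values were spread evenly over these draws, the share first abnormal at Week 16 is 1/5 = 20%. That is a ceiling under this assumption for cases missing from the Week 16 table, and the share missing from both analyses is smaller. The result depends on the assumption. Spreading onset evenly over time instead, with Weeks 12 to 16 as 4 of 16 weeks, gives 4/16 = 25%, while early clustering gives less. For platelets, protocol 1.2.4 reports Phase 2b decreases that levelled off at Week 4, which points below 20%.

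**The case against.** The strongest reply is that little is really lost.

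- **Other displays.** Laboratory values are listed (SAP 6.9 and 6.9.2). The same sentence in 6.9.2 also covers the monitoring criteria, some of which a single Week 16 value can meet (platelets, neutrophils, hemoglobin, AST/ALT). This stands: subjects do not vanish from the report, and a reader who infers that they do goes too far. But a monitoring row is a different count, and Appendix 4 lists no monitoring threshold for lymphocytes or creatinine.
- **Later values.** If the abnormality persists to the EOT visit, the retest and the EOT value form a pair in the End of Study data. This also stands. A reader might infer that every such case is lost from both analyses, and the timelines above do not support that. The reply does not restore the case to the Week 16 table, and it depends on an End of Study table that is not promised.
- **Reporting standards.** SAP 6.9.2 follows the sponsor's CaPS standards, and Appendix 2 ends by allowing safety analysis to follow them. They are not in the documents and might treat this differently. But the allowance is permissive, and no text says that it overrides the cut.
- **Not all laboratory rules need two values.** Correct. A single HBV DNA result above the limit of quantification is enough in the countries that test it (protocol 7.6.2.1), and Appendix 4 has a judgement-based criterion on withholding for more than 14 days. The point is confined to the threshold-based criteria. Scheduled on-treatment HBV DNA tests are at Week 12 and Week 20 or early termination, so the cut does not split them.
- **No effect on subjects or efficacy.** Correct. Retesting and stopping follow the protocol whatever the table counts.

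**Conclusion.** The point holds as a counting defect in one descriptive safety table. Applied literally, SAP Appendix 2 leaves a case first abnormal at Week 16 out of the Week 16 discontinuation-criteria table, which supports the final CSR. The case can be counted in neither analysis if the EOT value has recovered, or if the End of Study outputs omit this table.

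The number of subjects cannot be computed, because the documents give no rate at which these criteria are met. Under an even spread over the five draws, at most 1 in 5 cases arising in Weeks 2 to 16 would be missing from the Week 16 table. It would be wrong to read this as 20% lost altogether. The figure rests on an assumption that the documents do not support, and for platelets they point to a lower share. The conclusion also assumes that the retest is drawn after the day of the visit and that the cut is programmed as written. The correction is still worth making, because each such case is a mandatory stop and the change is small.

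**What to change.** Add to SAP 6.9.2, with a cross-reference in Appendix 2:

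> Laboratory criteria that need two sequential values are evaluated on the subject's complete laboratory series, without applying the Data Cut. Each case is counted once, in the analysis period and under the treatment in force at the first abnormal value. A case whose retest is not available at the Week 16 snapshot is listed as pending and resolved in the supplemental CSR.

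The cost is a few sentences of SAP text and a small programming change. There are two downsides. The Week 16 table would read a few retest records dated after the cut, an exception to the rule that it uses only data through the Week 16 visit. And a placebo subject whose retest follows the first PF-04965842 dose would be counted under placebo although confirmed on active drug, so these cases should be footnoted. No clinical rule and no efficacy analysis changes.
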